### **Analysis of all TEAE(s):**

The following TEAE summaries will be generated for the safety analysis set in each dose level.

- Overview of TEAEs, summarizing number of TEAE and number (%) of patients with any
  - TEAE
  - Related TEAE (including possibly related, probably related, or related)
  - Any TEAE  $\geq$ Grade 3
  - Serious TEAE
  - TEAE leading to death
  - TEAE leading to permanent treatment withdrawal
  - TEAE leading to ADCT-402 delay or reduction
  - TEAE with at least one infusion related reaction
- All TEAEs  $\geq$ Grade 3 by PT, showing number (%) of patients with at least one TEAE, sorted by decreasing incidence of PTs
- All TEAEs by primary System Organ Class (SOC) and PT, showing number (%) of patients with at least one TEAE, sorted by SOC in alphabetic agreed order and decreasing incidence of PTs within SOC. This sorting order will be applied to all other tables, unless otherwise specified.
- All TEAEs by primary SOC, PT and Maximal CTCAE grade, showing number (%) of patients with at least one TEAE, sorted by SOC and PT in alphabetic order. This sorting order will be applied to all other tables, unless otherwise specified.
- All TEAEs  $\geq$ Grade 3 by primary SOC, PT and Maximal CTCAE grade
- All related TEAEs by primary SOC, PT and Maximal CTCAE grade (including possibly related, probably related, or related)
- All TEAEs leading to treatment withdrawal by primary SOC, PT and Maximal CTCAE grade
- All TEAEs leading to dose delay by primary SOC, PT and Maximal CTCAE grade
- All TEAEs leading to dose reduction by primary SOC, PT and Maximal CTCAE grade

- All TEAEs leading to infusion interruption by primary SOC, PT and Maximal CTCAE grade
- All TEAEs with fatal outcome by primary SOC, PT and Maximal CTCAE grade
- All Serious TEAEs by primary SOC, PT and Maximal CTCAE grade
- All infusion related reaction TEAEs by primary SOC, PT and Maximal CTCAE grade
- Summary of grouped TEAEs selected by Standardised MedDRA Query (SMQ), ADCT modified SMQ will also be provided by primary Grouped term, PT and Maximal CTCAE grade. These group terms include: for effusion/edema, hepatic, fatigue, skin/nail, pain.
- Summary of TEAEs will also be provided by demographic factors including: sex, age group, race, disease subtype if appropriate.

All TEAEs, all serious adverse events (SAEs), all TEAEs leading to treatment withdrawal, all TEAEs leading to dose reduction, all TEAEs leading to dose delay, all TEAEs considered infusion related reactions, all TEAEs with fatal outcome and non-TEAEs will be listed.

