- 16.** Active second primary malignancy other than non-melanoma skin cancers, non-metastatic prostate cancer, *in situ* cervical cancer, ductal or lobular carcinoma *in situ* of the breast, or other malignancy that the Sponsor's medical monitor and Investigator agree and document should not be exclusionary.
- 17.** Any other significant medical illness, abnormality, or condition that would, in the Investigator's judgment, make the patient inappropriate for study participation or put the patient at risk.

Study Design:

This is a Phase 1, open-label, dose escalation (Part 1) and expansion (Part 2) study of the safety and tolerability of ADCT-402, used as monotherapy, in patients with relapsed or refractory B-NHL. The study will determine the MTD, as well as evaluate the preliminary activity, PK, pharmacodynamics (PD), and other exploratory assessments of ADCT-402.

In Part 1, patients will be assigned to treatment according to a 3+3 dose escalation design (see below) and with oversight by a Dose Escalation Steering Committee (DESC).

In Part 2, (expansion), all patients will be assigned to the recommended dose level(s) and schedule(s) of ADCT-402 identified in Part 1.

Estimated Duration of Patient Participation and Study Duration:

For each patient, the study will include a screening period (up to 28 days), a treatment period (until withdrawal), and a follow-up period to assess disease progression and survival for up to 12 months after the last dose of study drug. The total study duration will be dependent on overall patient tolerability to the study drug and response to treatment. It is anticipated that the duration of the entire study (Parts 1 and 2) could be approximately 3 years from first patient treated to last patient completed.

Patients who discontinue treatment for any reason other than disease progression will continue to be followed approximately every 12 weeks from the last disease assessment until disease progression, or initiation of new anticancer treatment. After documentation of disease progression or start of new treatment, patients will be followed (by telephone contact or chart review) approximately every 12 weeks for up to 12 months after the last dose of study drug to collect survival information.

Patients may withdraw from the study at any time and for any reason, without prejudice to their future medical care, by the Investigator or others at the study site.

Efficacy Assessments:

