7.6 Statistical Analysis Methodology

7.6.1 Safety Analyses

7.6.1.1 Analyses of Adverse Events

An AE will be considered to be a TEAE if it begins or worsens on or after first dose date and before last dose date + 84 days. Planned summaries of TEAEs are detailed in the statistical analysis plan and will include:

- All TEAEs.
- All serious TEAEs.
- All treatment-related TEAEs.
- All treatment-related serious TEAEs.
- All TEAEs resulting in study drug discontinuation.
- All DLTs.
- Other AE analyses of interest will be specified in the SAP.

The incidence of deaths and the primary cause of death will be summarized.

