## **4 Statistical methods**

All analyses use SAS® version 9.4 or higher. Summary tables will be organized by each dose level; if some dose levels have few patients, then dose levels could be combined into dose ranges. All available data will be used in the analyses, and important data will be included in data listings, sorted by dose level, patient, and by visit within patient. Missing data will not be imputed, except via censoring in survival analyses and as otherwise specified.

Unless otherwise noted, categorical data will be presented using counts and percentages, with the number of patients in the analysis set by treatment group as the denominator for percentages. Percentages will be rounded to one decimal place, except 100% will be displayed without any decimal places and percentages will not be displayed for zero counts. Continuous data, unless otherwise noted, will be summarized using the number of observations (n), mean, standard deviation (std), median, minimum, and maximum. Minima and maxima will be rounded to the precision of the original value, and means, medians, and 95% confidence intervals (CIs) if presented will be rounded to 1 decimal place greater than the precision of the original value. The std will be rounded to 2 decimal places greater than the precision of the original value, up to a maximum of 3 decimal places.

No hypothesis testing will be performed in this study.

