### **4.1 Analysis Sets**

#### **4.1.1 Safety Analysis Set**

The safety analysis set consists of all patients who receive ADCT-402.

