### 4.8.2 Adverse Events, Serious Adverse Events, and Deaths

#### 4.8.2.1 Analyses of adverse events

The primary focus of adverse event reporting will be on TEAEs. An adverse event (AE) will be considered to be a TEAE if it begins or worsens on or after first dose date and until 84 days (12 weeks) after the last dose date, or start of a new anticancer therapy/procedure, whichever comes earlier.

An AE occurring before the first dose or more than 84 days (12 weeks) after last dose date or after the start of a new anticancer therapy/procedure will not be included in TEAE displays, but will be listed as non-TEAEs.

If an AE date/time of onset (occurrence, worsening, or becoming serious) is incomplete, an imputation algorithm will be used to classify the AE as pre-treatment, TEAE, or post-treatment. The algorithm for imputing date/time of onset will be conservative and will classify an AE as a treatment-emergent unless there is definitive information to determine it is a non-TEAE (pre- or post-treatment).

Details on classification of AEs with missing or partial onset dates are provided in Section 6.

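### TEAE percentages by dose level are crude counts over windows that lengthen with treatment, so when durations differ the by-dose safety picture can be distorted; a fixed-window table should be added.

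*SAP*

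**What the plan says.** **Window.** Under SAP 4.8.2.1 an AE is treatment-emergent if "it begins or worsens on or after first dose date and until 84 days (12 weeks) after the last dose date", or until a new anticancer therapy or procedure starts, whichever is earlier. Protocol 7.6.1.1 has the same 84-day extension ("begins or worsens on or after first dose date and before last dose date + 84 days") without the new-therapy cut.

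**Measure.** SAP 4.8.2.1 introduces the tables with "The following TEAE summaries will be generated for the safety analysis set in each dose level". The first is an "Overview of TEAEs, summarizing number of TEAE and number (%) of patients with any" of a list of event types, and the rest are counts or percentages of patients by term and grade. SAP 4 sets the denominator: "with the number of patients in the analysis set by treatment group as the denominator for percentages". SAP 4.1.1 defines the population: "The safety analysis set consists of all patients who receive ADCT-402". The denominator is therefore patients, whatever their time under observation.

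**Duration and schedule.** Treatment continues until withdrawal (Protocol 3.1). The regimens in Protocol 3.1 are every 3 weeks throughout, every 3 weeks for two cycles and then every 6 weeks, or every 6 weeks from the start. More than one schedule is listed at 120, 150 and 200 µg/kg, and the SAP organises tables by dose level.

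**Related output.** Duration and number of cycles are tabulated by dose level in a separate exposure summary (SAP 4.7.1). DLTs have a one-cycle observation period but are only listed, and only for Part 1 (SAP 4.8.1). The adverse event section contains no fixed-window, by-cycle, patient-time or time-to-first-event summary.

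**The concern.** A percentage of patients with at least one event depends on both the event rate and the time during which events are counted. Here that time is tied to treatment. On the alternative schedules patients continue only with at least stable disease. Progression, recurrent Grade 3 or 4 non-hematologic toxicity and long delays are grounds for ending treatment (Protocol 4.2.1). Activity therefore tends to lengthen the window and toxicity to shorten it, and both may vary with dose.

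Reading across the dose columns can then exaggerate, flatten or reverse a dose-toxicity pattern. Safety parameters in both parts are a primary endpoint (Protocol 7.2.1). With no hypothesis testing planned (SAP 4), reading across the columns is how doses will be compared.

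**Working it through.** The plan states no TEAE rate or expected duration, so there is no figure of its own to reproduce. The hazards and numbers of infusions below are assumptions.

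**1. Window length.** With a complete tail, W = (number of infusions − 1) × interval + 84 days. These are maxima, since new therapy can end the window sooner. For 3-week dosing:

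| Infusions | W (days) | W (months of 30.44 days) |
|---|---|---|
| 1 | 84 | 2.76 |
| 2 | 21 + 84 = 105 | 3.45 |
| 4 | 63 + 84 = 147 | 4.83 |
| 5 | 84 + 84 = 168 | 5.52 |
| 8 | 147 + 84 = 231 | 7.59 |

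**2. Crude percentage at constant hazard h:** P = 1 − exp(−hW).

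- Equal toxicity, h = 0.10 per month. Two infusions: 1 − exp(−0.345) = 29%. Eight: 1 − exp(−0.759) = 53%.
- 1.5 times the hazard (0.15) for two infusions: 1 − exp(−0.517) = 40%. This is below the 53% of the less toxic dose given eight times.
- The same 40% against four infusions at 0.10: 1 − exp(−0.483) = 38%. The order is correct.
- Against five infusions at 0.10: 1 − exp(−0.552) = 42%. The order is reversed.

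**3. Condition for reversal.** The briefly given dose looks safer when the window ratio exceeds the hazard ratio. The ratios to two infusions are 147/105 = 1.4 for four, 168/105 = 1.6 for five and 231/105 = 2.2 for eight. A hazard ratio of 1.5 lies between the first two.

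**4. Range over the assumed risk.** Setting h from an assumed 84-day risk, for two versus eight 3-week infusions:

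| 84-day risk | Equal toxicity, 2 vs 8 | 1.5× given twice vs 1× given eight times |
|---|---|---|
| 15% | 18.4% vs 36.0% | 26.3% vs 36.0% |
| 30% | 36.0% vs 62.5% | 48.8% vs 62.5% |
| 50% | 58.0% vs 85.1% | 72.7% vs 85.1% |

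**5. Sensitivity, 30% case.**

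- Random numbers of cycles with means 2 and 8: equal toxicity 35.5% vs 56.2%; 1.5× brief vs 1× long 48.0% vs 56.2%.
- Half the 84-day risk in the first 21 days: 34.0% vs 53.8%, and 46.4% vs 53.8%.
- Both groups cut at 30 days after last dose by new therapy: equal toxicity 19.5% vs 52.8%.
- All risk in the first 21 days: no distortion.

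**6. Fixed window from first dose.** At 0.10 versus 0.15 per month, 42 days (1.38 months) gives 1 − exp(−0.138) = 13% versus 1 − exp(−0.207) = 19%. At 84 days it gives 24% versus 34%. The order is correct and equal toxicity gives equal percentages.

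**7. Small cohorts.** Take the 30% case, two versus eight infusions, and the chance that the 1.5× dose shows fewer affected patients (two independent binomials). With 10 per group it is 66% on crude percentages and 22% with a fixed 84-day window. With 20 per group it is 77% and 18%. With a 42-day window the risks are 16.3% and 23.5%, and the chance is 24% and 22%.

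**8. Rate per patient-month.** Suppose the on-drug hazard of the 30% case (0.00425 per day) and no risk beyond 21 days after last dose, with the whole 84-day tail still counted as time at risk. Two infusions carry 42 days of risk: 16.3% affected over a mean 91.2 days (3.00 months), or 5.5 per 100 patient-months. Eight carry 168 days: 51.0% over 151.0 days (4.96 months), or 10.3. The 1.5× dose given twice: 23.5% over 85.1 days (2.79 months), or 8.4. Equal toxicity again looks unequal, and the more toxic dose again looks safer.

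**The case against.** Crude tables are customary in phase 1, the analyses are descriptive, and the separate exposure summary lets a reader see unequal durations. Laboratory, ECG and vital-sign changes are summarised by scheduled assessment, and DLTs have a one-cycle window. These points bear on priority. They do not remove the problem: seeing unequal durations corrects no percentage, the exposure duration leaves out the 84-day tail, and the SAP only lists DLTs.

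A reader might infer that the MTD or the choice of Part 2 dose is compromised. The documents do not support that. The MTD follows from cycle-1 DLTs (Protocol 3.2). The steering committee sets Part 2 doses from accumulating safety, efficacy and pharmacokinetic data, with review at least monthly (Protocol 3.1 and 6.3.1.1). No section makes a crude TEAE percentage an input to either decision.

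A reader might also extend the illustration to eight 6-week infusions: 7 × 42 + 84 = 378 days, or 71% at 0.10 per month. That does not match the regimens. The listed 6-week schedules at 200 µg/kg move to 60 µg/kg after one or two cycles, so one constant hazard over eight infusions is not a fair model. SAP 3.3 also says that only a few patients received that 6-week schedule.

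Precision is a fair objection. Dose levels in Part 1 are generally capped at 10 patients unless responses are seen (Protocol 3.2), and Part 2 cohorts are about 10 to 20 (Protocol 7.3). The exact 95% interval for 5 of 10 is 19% to 81%. Even a fixed window misorders the doses about one time in five in the example. It removes the bias but leaves the sampling error.

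**Conclusion.** The point holds in a limited form. The window, the per-patient denominator and the absence of any adjustment stand in the text. Distortion requires that durations differ between dose levels and that risk is not confined to early cycle 1. Reversal further requires the window ratio to exceed the hazard ratio. In the worked case the order is wrong against five or more infusions of the less toxic dose and right against four.

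The size is illustrative. It rests on assumed hazards, constant except in the sensitivity runs, and on assumed numbers of infusions; the base calculations also assume complete 84-day tails. What is affected is the by-dose reading of the TEAE tables, a primary safety endpoint in both parts. It is worth changing because the remedy needs only data already collected.

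**What to change.** Add one table to SAP 4.8.2.1, by dose level and schedule. It should cover the overview rows (Grade 3 or higher, serious, leading to withdrawal, delay or reduction) and the grouped terms. For each, give the percentage of patients with first onset within 42 days of first dose, and optionally also within 84 days to capture later onset. Report beside it how many patients died, dropped out or started new therapy before the window closed. State that comparisons between doses rest on this table, and keep the crude tables as the full record.

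The cost is one table from onset and dosing dates already collected. It misses later events. A 42-day window also holds two 3-week infusions but only one 6-week infusion, which a footnote should say.

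A rate per patient-month may be shown as a supplement, provided its time at risk is not dominated by the 84-day off-drug tail. It should not be the basis for comparing doses, because with the full tail counted it can recreate the same fault.

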#### **4.8.2.2 Deaths**

The following deaths summaries will be generated on the safety analysis set.

- Number (%) of patients who died during the study and reasons for death
- Number (%) of patients who died within 30 days after last dose of study drug except deaths occurred after taking any subsequent anticancer therapy/procedure and reasons for death

All deaths will be listed.

#### **4.8.3 Laboratory Data**

Laboratory data of hematology, biochemistry, coagulation, and additional renal function studies up to 84 days after last dose of study drug or the end of treatment visit date, whichever is later, will be reported in SI units. Descriptive statistics (mean, standard deviation, median, and range) will be calculated for the raw data and for their changes from baseline at each scheduled assessment.

All results will be summarized using shift from baseline. Shifts for clinical laboratory results that can be graded according to CTCAE version 4.0 will be summarized by CTCAE grade.

Summaries by visit will include data from scheduled assessments, and all data will be reported according to the nominal visit date for which it was recorded. Unscheduled data will be included in “worst case post-baseline” summaries, which will capture a worst case across all scheduled and unscheduled visits after the first dose of study treatment.

Summary analyses will include data up to the start of subsequent anticancer therapy/procedure.

All laboratory data, including urinalysis, will be listed. Pregnancy test results will not be listed, but will be included in datasets.

#### **4.8.4 Electrocardiogram**

Electrocardiogram (ECG) parameters (e.g., QTc in ms) will not be converted or derived, but will be reported as provided by investigational sites.

Descriptive statistics (mean, standard deviation, median, and range) will be calculated for the raw data and for their changes from baseline at each scheduled assessment.

The following abnormal QTc (including QTcF, QTcB and QTc with unspecified method) will be reported:

At any post-baseline with absolute value

>450 - <=480 ms

>480 - <=500 ms

> 500 ms

Change from Baseline

>30 – <=60 ms

>60 ms

For patients with unspecified QTc method at either baseline or post-baseline, consistent correction method is assumed within a patient when calculating the change from baseline.

Summary analyses will include data up to the start of subsequent anticancer therapy/procedure.

All ECG data will be listed, both for quantitative data and for overall impression.

#### **4.8.5 Vital Signs**

Descriptive statistics (mean, standard deviation, median, and range) for vital signs data, including systolic and diastolic blood pressure, heart rate, respiration rate, and body temperature will be calculated for the raw data and for their changes from baseline at each scheduled assessment.

Summary analyses will include data up to the start of subsequent anticancer therapy/procedure.

All vital signs data will be listed together with body weight and ECOG performance score.

#### **4.8.6 ECOG Performance Status**

ECOG performance score data will be listed together with vital signs and body weight.

#### **4.8.7 Physical Examinations and Body Weight**

Physical examination will be performed according to protocol. Clinically significant findings from the physical examinations will be recorded as medical history (prior to first administration of ADCT-402) or AEs (subsequent to first administration of ADCT-402).

Body weight will be listed together with vital signs and ECOG performance score.

## 4.9 Efficacy Analyses

Disease assessment will be performed according to protocol. The endpoints described in this section use the investigator's evaluation according to the Lugano Classification criteria and clinical progression from End of Treatment (EOT)/Study disposition page.

Lesion assessment data (target lesions, non-target lesions, and new lesions) will be listed. A separate listing will contain derived data for DOR, PFS, and OS.

### 4.9.1 Overall Response Rate

Overall response rate is defined as the proportion of patients who achieve either CR or PR as best overall response as assessed by investigators according to the Lugano Classification criteria before the start of subsequent anticancer therapy or procedure.

The order of overall response category is: CR, PR, SD, NE, PD (including disease recurrence/relapse). The overall response category will be derived based on response assessment performed on or before the start of subsequent anticancer therapy/procedure. Patients without documented subsequent anticancer therapy and/or with missing start date of anticancer therapy will be considered as not having received subsequent anticancer therapy. If a patient only has one valid disease assessment which is SD, and the assessment is within 35 days after the first dose, the overall response for this patient will be considered as NE.

The overall response rate and the corresponding 95% two-sided exact confidence interval at each dose level will be presented. Subgroup analysis may be provided for disease subtype, disease stage, double/triple hit (yes/no), bulky disease (yes/no), age group, sex, country, response to the first line and/or most recent line of prior systematic therapy (relapse: CR+PR vs. refractory: SD+PD vs. other: NE + missing), and other relevant variables.

Percent change from baseline in the sum of product of diameters (SPD) for target lesions will be presented for available data in the efficacy analysis set by dose level. These data will also be displayed as a waterfall plot, with vertical bars representing the sorted values of best percent reduction for each patient.

Tumor response and lesion measurement will be listed by assessment visit.

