4.1.2 Day 1 of Each Cycle

The following procedures will be performed prior to ADCT-402 infusion (unless otherwise indicated) at each cycle, unless otherwise specified.

- Blood or urine β -HCG pregnancy test required if the pregnancy test was obtained >7 days prior to Day 1 (every other cycle).
- Physical examination including whole body skin assessment, unless an assessment was performed within 3 days prior to Day 1.
- Vital signs: On Day 1 of Cycles 1 and 2, vital signs are to be measured before the start of the ADCT-402 infusion, every 30 minutes during the infusion, at the end of infusion, and at 1, 3, and 6 hours after the end of infusion. If no clinically significant changes occur during Cycles 1 and 2, vital sign measurements are to be obtained prior to infusion start and end of infusion for all subsequent infusions. If clinically significant changes in vital signs are observed at Cycle 1 and/or 2 infusion, that patient will be required to have vital signs measured before the start of the ADCT-402 infusion, every 30 minutes during the infusion, at the end of infusion, and at 1, 3, and 6 hours after the end of the ADCT-402 infusion for all subsequent cycles.
- Weight.
- ECOG performance status.
- Samples for hematology, coagulation panel, biochemistry parameters, will be measured prior to dosing unless the last sample was collected:
 - <24 hours before the start of ADCT-402 infusion on Day 1 of Cycle 1, or
 - <72 hours before the start of ADCT-402 infusion on Day 1 of Cycle 2 and subsequent cycles.

- Sample collection for additional renal function studies.
- Sample collection for urinalysis

Prior to dosing unless the last sample was collected:

- <24 hours before the start of ADCT-402 infusion on Day 1 of Cycle 1, or
- <72 hours before the start of ADCT-402 infusion on Day 1 of Cycle 2 and subsequent cycles.

- Disease assessment:

Patients Initially Treated Every 3 weeks

- To be conducted within 6 days prior to Day 1 of Cycles 3 and 5 and thereafter every third cycle (i.e., Cycles 8, 11, 14, etc.), until disease progression, or more frequently, if clinically indicated.
- Patients who initially follow a three-week dose schedule and then transition to a six-week schedule following Cycle 2 should have disease assessments ~6 weeks after Cycle 1 Day 1, and ~12 weeks after Cycle 1 Day 1, and thereafter at least every 12 weeks.

Patients Initially Treated Every 6 weeks

[figure not shown]

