6.1 Efficacy Assessments

Disease assessments will occur every other cycle for the first 2 evaluations (6 weeks [end of Cycle 2 \pm 1 week] and 12 weeks [end of Cycle 4 \pm 1 week]), and every third cycle (every 9 weeks [e.g., end of Cycles 7, 10, 13, etc., \pm 1 week]) thereafter until progression, or more frequently, if clinically indicated.

Patients Initially Treated Every 3 weeks

- To be conducted within 6 days prior to Day 1 of Cycles 3 and 5 and thereafter every third cycle (i.e., Cycles 8, 11, 14, etc.), until disease progression, or more frequently, if clinically indicated.

Patients who initially follow a three week dose schedule and then transition to a six week schedule following cycle 2 should have disease assessments ~6 weeks after Cycle 1 Day 1, ~12 weeks after Cycle 1 Day 1, and thereafter at least every 12 weeks.

Patients Initially Treated Every 6 weeks

- For patients who have reduced dosing frequency and are following a 6 week schedule, disease assessments should occur approximately 6 weeks and 12 weeks after Cycle 1 Day 1, and thereafter at least every 12 weeks. It is understood that there will be a \pm 6 day window for restaging of these patients.

For patients in Part 2: Treatment continuation will require independent verification of the local response assessment unless otherwise approved by the sponsor.

Assessments may be performed within \pm 1 week of the required timepoint and response assessment must be available prior to initiation of dosing at the subsequent cycle.

In case of dose delays, disease assessment should be maintained at the frequencies defined above and response assessment is required prior to resumption of ADCT-402 dosing (only if the interval from last scan is \geq 6/9/12 weeks, as applicable) to rule out disease progression.

The patient's response to treatment will be determined by the Investigator as complete response (CR), partial response (PR), stable disease (SD), or progressive disease (PD), based on the 2014 Lugano Classification Criteria ([Appendix 12.2](#)). Images will be obtained according to local site imaging requirements and may be required to be submitted for a central/independent review. Submission instructions for the central/independent review will be provided in a separate manual.

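### The 35-day rule for stable disease depends on how many assessments a patient has, so an early SD followed by documented progression is classed as SD, above the NE given to an early SD alone

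*SAP*

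**What the plan says.** SAP 4.9.1 defines ORR as "the proportion of patients who achieve either CR or PR as best overall response", by investigator assessment under the Lugano criteria. It ranks the categories as follows: "The order of overall response category is: CR, PR, SD, NE, PD (including disease recurrence/relapse". The data that feed the ranking are described thus: "The overall response category will be derived based on response assessment performed on or before the start of subsequent anticancer therapy/procedure".

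One time condition is placed on SD. It opens "If a patient only has one valid disease assessment which is SD, and the assessment is within 35 days after the first dose" and concludes that "the overall response for this patient will be considered as NE". The Protocol's ORR definition (7.6.2.1) and its Lugano appendix (12.2) set no minimum time for SD.

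For patients on 3-weekly dosing, Protocol 4.1.2 times the first assessments this way: "To be conducted within 6 days prior to Day 1 of Cycles 3 and 5". Protocol 6.1 repeats this and lets scanning continue "until disease progression, or more frequently, if clinically indicated". It also describes the first evaluation as at 6 weeks, plus or minus 1 week.

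**The concern.** The rule treats an SD within 35 days as insufficient when nothing follows it. What follows can be bad news, and the rule then stops applying. A patient with an early SD and no later scan is NE. A patient with the same early SD and a later PD is SD, because SD ranks above both NE and PD. The second patient has done no better, and the only SD on record is the one that did not suffice for the first.

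The misclassification runs in one direction. It can add patients to SD and cannot remove any. At stake is the reading of disease control at small dose levels, in a study with no hypothesis test (SAP 4) where category counts would be read at face value.

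**Working it through.** No sample size, power or error rate is involved. The check applies the rule to example sequences and then asks whether the schedule permits them.

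**1. The rule applied.** Inputs, all from SAP 4.9.1: exactly one valid assessment, which is SD at day 35 or earlier, gives NE; otherwise take the best category in the order CR, PR, SD, NE, PD. Days are counted after first dose, and day 35 is taken as inside the limit. Each assessment is assumed valid and made before subsequent therapy. The third column disregards any SD at day 35 or earlier, and gives NE if nothing else remains.

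| Assessments | SAP as written | Minimum applied to every SD |
|---|---|---|
| SD day 30 | NE | NE |
| SD day 35 | NE | NE |
| SD day 36 | SD | SD |
| SD day 30, PD day 50 | **SD** | PD |
| SD day 20, PD day 34 | **SD** | PD |
| SD day 30, SD day 84 | SD | SD |
| SD day 30, PR day 84 | PR | PR |
| PD day 30 | PD | PD |

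The fifth row is the clearest case: the patient has progressed before the 35-day threshold and is still SD. The anomaly is confined to an early SD followed by PD, or by an NE assessment if the SAP regards that as valid. A later SD or response is classified sensibly.

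If the early SD were instead recoded to NE and the SAP order kept, the two bold rows would become NE, because NE ranks above PD.

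**2. Can a first SD fall by day 35?** For 3-weekly dosing, Cycle 3 Day 1 is nominally 2 × 21 = 42 days after first dose.

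- Scan up to 6 days before it (Protocol 4.1.2): 42 − 6 = 36, so days 36 to 42 nominally. Outside the rule.
- One-week allowance (Protocol 6.1): 42 − 7 = 35. Inside.
- Cycle 3 Day 1 moved 3 days earlier (window in Protocol 12.1.1): 42 − 3 − 6 = 33. Inside.
- Two consecutive 18-day cycles: 2 × 18 − 6 = 30. Inside. This assumes that the 3-day window applies to each cycle in turn. The SAP's example of an important deviation is a cycle starting less than 18 days after the last.
- Clinically indicated scans: any earlier day.

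For 6-weekly dosing, the 6-day window stated for those patients gives 42 − 6 = 36 at the earliest, outside the rule.

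**3. Which outputs change.**

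- ORR: no change. SD, NE and PD are all non-response.
- DOR: no change. It covers responders only.
- PFS: no change. It uses the date of progression or death.
- OS: no change. It uses the date of death.
- Overall response category: changes, as do any counts drawn from it.

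**4. Size.** One patient in a dose level of 10 is 1/10 = 10 percentage points of SD. In a cohort of 20 it is 1/20 = 5 points. Ten is the Part 1 cap per dose level unless at least 3 respond (SAP 3); Part 2 cohorts are about 10 to 20 (Protocol 7.3).

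**The case against.** The best defence is that this is a follow-up rule and sets no minimum duration for SD. Day 35 is the lower edge of the 6-week scan window, and a patient scanned again has been followed. Neither the Protocol nor its Lugano appendix requires SD to last any set time, so an investigator's SD can stand as the best category. This bars the inference that the SAP holds every SD before day 36 to be invalid; the text covers only the lone early SD. It does not explain why documented progression should place a patient above NE.

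Three further points stand.

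- **No planned estimate is biased.** A reader might infer that the response rate or a planned SD rate is wrong. SAP 4.9.1 commits to ORR with an exact interval, SPD change, a waterfall plot and listings. It names no best-response table and no disease-control rate. Such a table is likely, since all five categories are defined, but it is an inference.
- **PD is not shown to be understated.** A reader might infer that PD falls by the same 10 points. That holds only against a scheme that calls these patients PD. With NE ranked above PD, recoding the early SD alone gives NE and leaves the PD count where it was.
- **The progression is not hidden.** It is a PFS event, and responses are listed by visit.

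The effect also needs the progression to be a valid disease assessment. SAP 4.9 also takes clinical progression from the end-of-treatment or disposition page, and 4.9.1 does not say whether that counts. If it does not, the patient stays NE.

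**Conclusion.** The rule is wrong as written, in a minor way. An early SD followed by a PD assessment before subsequent therapy is classed as SD, although the same SD alone is NE. The effect is limited to the derived overall response category and any SD, NE or PD counts taken from it.

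Few patients are likely to be affected, because the nominal first scan falls after day 35. The documents give no expected number. The 10 points is the weight of one patient in ten and not a forecast; SAP 4 also allows sparse dose levels to be combined, which would dilute it.

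The conclusion rests on a literal reading of the single-assessment condition and on the progression counting as a valid assessment.

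**What to change.** Replace the single-assessment condition in SAP 4.9.1 with a condition on SD itself:

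- SD counts as best overall response only if SD or better is documented more than 35 days after first dose.
- Otherwise, an early SD followed by PD before subsequent therapy is PD, notwithstanding the ranking of NE above PD. PD here includes radiographic progression and clinical progression at end of treatment or end of study.
- An early SD followed by nothing, or only by NE, is NE.

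The second line is needed because recoding the early SD to NE would, under the present order, leave the patient NE.

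The cost is a short SAP edit and a change to the derivation program, with no new data. The SD share may become slightly less favourable. A patient scanned at day 33 inside the permitted window, with progression at the 12-week scan, would become PD although control may have lasted beyond day 35. The sponsor should accept that trade-off knowingly.
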